5.2 Regulatory Authorities

Prior to the initiation of the trial all relevant documents as required by the national legislation will be submitted to the regulatory authority(ies) (RA) responsible for the trial approval in the respective country.

In accordance with the national drug law all approvals needed for conducting the trial in the respective country will be obtained.

5.3 Protocol Modification

Substantial amendments to the conduct of the clinical trial may arise from changes to the protocol or from new information related to the scientific background of the trial.

All amendments must be discussed and signed by the sponsor/its representative, [REDACTED] and the coordinating investigator prior to implementation.

Amendments to the trial are regarded as “substantial”⁵ where they are likely to have a significant impact on:

- the safety or physical or mental integrity of the patients, or
- the scientific value of the trial.

In all cases, an amendment is only to be regarded as ‘substantial’ when one or both above criteria are met.

When the sponsor/its representative intends to make a substantial amendment to the protocol that would meet the above-mentioned criteria, he should notify [REDACTED]. The sponsor/its representative authorizes [REDACTED] to supervise all necessary notifications to the ECs and RAs and to receive all approvals needed before an amendment is implemented.

Amendments which might have an impact on the safety, physical or mental integrity of the patients (and/or could influence on the patients’ decision to participate in the trial) require new patient information and a new informed consent/ assent form that is to be signed by all patients enrolled in the trial who are affected by the amendment.

In case of minor changes to the protocol (administrative, logistical), the non-substantial amendment will be prepared and signed by both [REDACTED] and sponsor or its representative. A written approval of sponsor/its representative before implementation is required, however not from ECs and RAs.

5.4 Patient Information and Informed Consent

Before being enrolled into the trial, patients must have consented to participate in response to a complete written and verbal explanation of the nature, scope and possible consequences of the trial by a physician in a form and language understandable to them.

The patients must be able to understand the full implications of their decision.

The patient information and informed consent will be prepared by [REDACTED] and will be translated into the respective local language of the clinical center(s) whereby the translated documents will be used for confirmation of the patient's consent by the signature of the investigator, the patient and in case of adolescents by the signatures of the parent(s)/ guardian(s).

For adult patients (≥18 years) the informed consent to participate in the trial must be provided in written form.

For adolescent patients (≥14 - <18 years) the own subject informed consent/ assent to participate in the trial must be provided in written form with the mandatory written informed consent from all parent(s)/ legal guardian(s).

The patient information and informed consent will explain the nature of the trial, its objectives and potential risks. Both the informed consent discussion and the written informed consent form and any other written information to be provided to patients will include explanations of the points mentioned in section 4.8.10 of the ICH Guidance on Good Clinical Practice E6(R2) (CPMP/ICH/135/95)³.

Personal information will be treated as strictly confidential and will not be publicly available.

As required by the ICH-GCP guideline, the patient authorizes in written form that the patient's original medical records may be verified by the CRA(s), the auditor(s), and the regulatory authorities by direct access in accordance with the applicable laws and regulations.

As required by the ICH-GCP guideline, the trial specific information for patients and informed consent will be received as one original and enough ample time will be given to the patients to read the document. The personally signed and dated original will remain with the investigator as part of the confidential data and will be kept there (in the ITF) for at least 25 years after the trial has been completed. A certified copy of the personally signed and dated original will be handed over to the patient.

To ensure medical confidentiality and data protection, the patient identification and all other essential documents as addressed in chapter 8 of the ICH-GCP guideline will be located in the ITF and must be archived for at least 25 years after the trial has been completed (please refer to protocol sections 9.5.3, 11.1 and 11.7).

The individual medical health records/ files of the clinical center(s) shall be kept for the maximum period of time permitted by the national law of the country of the clinical center. Image carriers or other data carriers can be used for storage.

The investigator will allow these documents to be inspected on request and will affirm - by signing and dating - in the case report forms that informed consent has been obtained before start of any trial-related procedure(s).

The investigator will not undertake any investigations specifically required only for the trial until valid consent has been obtained.

5.5 Patient Insurance

Every subject is insured in accordance with the provisions of the national law of the countries involved against damage to health which might occur during the conduct of the clinical trial and the material damages which might occur in connection thereto.

Excluded from the insurance cover are damages to health and worsening of previous existing diseases which would have occurred or continued if the patient had not taken part in the clinical trial. Following the clauses of the insurance, the insured patients are to be informed about the existence of the insurance contract.

A copy of the insurance certificate will be filed in the investigator's trial file (ITF).

5.6 Patient's Confidentiality

To maintain patient's confidentiality, all data recorded during the trial will be identified by patient's screening/ randomization number and patient's date of birth. However, the investigator agrees to record the complete patient identification. This information will be treated with strict adherence to confidentiality and will be filed in the investigator's trial file (ITF).

6 Introduction

6.1 Acute Rhinosinusitis

Acute rhinosinusitis (ARS) is a very common condition that is primarily managed in primary care. Prevalence rates vary from 6-15% depending on the study parameters, although studies specifying ARS report 6-12%, with a prevalence of recurrent ARS estimated at 0.035%.

The primary causes of ARS are viruses with 0.5-2.0% of patients developing acute bacterial rhinosinusitis secondary to a viral infection. Prevalence of ARS varies with season (higher in the winter months) and climatic variations, and increasing with a damp environment and air pollution (European Position Paper on Rhinosinusitis and Nasal Polyps; Fokkens et al., 2012¹²).

ARS in adults is defined as:

[figure not shown]
Sudden onset of two or more symptoms:

- nasal blockage/ obstruction/ congestion
- or nasal discharge (anterior/posterior nasal drip)
- ± facial pain/pressure
- ± reduction or loss of smell

for <12 weeks.

ARS can be sub-divided into “acute viral rhinosinusitis (synonymous with “common cold””, in which the duration of symptoms is less than 10 days, usually a self-limiting condition that frequently does not present to clinicians, and “acute post-viral rhinosinusitis”, defined by an increase in symptoms after 5 days or persistence beyond 10 days.

Typical symptoms of spontaneous rhinovirus infections peak at days 2 to 3 and wane thereafter but may persist 14 days or longer. Symptoms of viral rhinosinusitis may persist for longer than 10 days, but they gradually decrease in severity (see figure below taken from Rosenfeld et al., 2015¹³; US Clinical Practice Guideline on Adult Sinusitis).

According to the German Society of General Practice/Family Medicine (DEGAM, 2017¹⁴), viral rhinosinusitis episodes are clinically cured after a maximum of three weeks.

A clinician should diagnose acute “bacterial” rhinosinusitis (ABRS) when symptoms or signs of acute rhinosinusitis persist without evidence of improvement for at least 10 days beyond the onset of upper respiratory symptoms.

Fever is present in some patients with viral rhinosinusitis in the first few days of illness but does not predict bacterial infection as an isolated diagnostic criterion. Fever has a sensitivity and specificity of only about 50% for ABRS.

Adjunctive treatments for rhinosinusitis that may aid in symptomatic relief include analgesics, decongestants (α -adrenergic), corticosteroids, saline irrigation, and mucolytics. None of these products has been specifically approved by the FDA for use in ARS (as of March 2014), and only some have data from controlled clinical studies supporting this use. Moreover, existing trials often include co-interventions and a heterogeneous population of patients with viral, recurrent bacterial, chronic, and allergic rhinosinusitis.

With regard to mucolytics the “European Position Paper on Rhinosinusitis and Nasal Polyps¹²” states:

“Mucolytics are used as adjuncts to antibiotic and/or decongestant treatment in ARS in order to reduce the viscosity of sinus secretion. Although some drugs have been shown to have mucolytic effect and were recommended as adjunct treatment for ARS, the benefit of such treatment is not clear due to the lack of standardization in pharmacodynamic and pharmacokinetic properties of these drugs, and also double-blinded, placebo-controlled (DBPC) randomized studies to prove their efficacy. In future, more standardization of mucolytics and larger scale DBPC randomized studies still need to be done in order to fully assess the efficacy of mucolytics in the treatment of ARS.”

This position is also transparent in the current guideline on rhinosinusitis of the “German Society of General Practice/Family Medicine” (DEGAM, 2017), stating that mucolytics like acetylcysteine or ambroxol are commonly used as adjunctive therapies, although the benefit of these medications lacks clinical evidence.

6.2 Mode of Action of Acetylcysteine

Acetylcysteine (NAC) is the N-acetyl derivative of the amino acid L-cysteine and a precursor in the formation of the antioxidant glutathione in the body. The thiol (sulfhydryl) group confers antioxidant effects and is able to reduce free radicals. The mucolytic activity of NAC is considered to be dual in origin:

- (1) its sulfhydryl group breaks the disulfide bonds between the mucopolysaccharide fibers, and
- (2) disrupts polymerization bonds of DNA fibers (in purulent mucus).

These mechanisms are thought to decrease the viscosity of the mucus.

Oral preparations containing up to 600 mg of NAC as a single dose have been marketed by pharmaceutical companies within the EU to a large extent for many decades, with recognized efficacy and proven safety in the mucolytic treatment of lower respiratory pathologies such as acute and chronic bronchitis and related diseases.

6.3 Clinical Use of Acetylcysteine for Indication Sinusitis

Pharmacotherapeutic group: Cough and cold preparations; Mucolytics (SmPC ACETYLCYSTEINE 600 MG EFFERVESCENT TABLET¹⁵)

ATC code: R05CB01

Therapeutic indications: Secretolytic therapy in acute and chronic bronchopulmonary diseases accompanied by impaired formation and transport of mucus in adults and adolescents from 14 years of age.¹⁵

The upper and the lower respiratory tracts constitute a continuum, in particular with respect to the histological structure of the epithelium and of the secretory cells. There is parallelism in the pathologies of upper and lower airways:

Thus we find comparable symptoms of cellular inflammation with a predominance of eosinophilia in bronchial asthma and allergic rhinitis.

Likewise, there are analogies between acute and chronic bronchitis and rhinosinusitis, in which the neutrophilic inflammation is predominant.

Given the well-established use of acetylcysteine in bronchitis, it makes sense to pursue this therapeutic approach in rhinosinusitis as well. Indeed the first clinical investigations were reported more than 50 years ago. In a study of 32 sinusitis patients treated with a NAC solution administered by sinus irrigations, the authors concluded that NAC is an effective mucolytic agent (Komet et al.¹⁶, 1965). About 20 years later Boner et al. (1984)¹⁷ conducted a study in children for the treatment of sinusitis with NAC administered intramuscularly in combination with an antibiotic. In a publication by Zeiger (1992)¹⁸ on "Prospects for ancillary treatment of sinusitis in the 1990s" the author stated that based on the apparent efficacy and relative safety of oral NAC in chronic bronchitis, "controlled" trials investigating its use in the treatment of chronic sinusitis should be encouraged. However also a more recently published phase 3 study in the indication of recurrent acute sinusitis did not meet the expectations for a recommendation of mucolytics in the current treatment guidelines for rhinosinusitis. This study, reported by Macchi et al. (2012)¹⁹, employed only a single-blind design and NAC or the comparator substance were given in addition to the basic therapy of a nasal corticosteroid. Besides a very small sample size, a study reported by Bahtouee et al. (2017)²⁰ revealed even more weaknesses by adding NAC to amoxicillin-clavulanic acid, pseudoephedrine, and intranasal normal saline.

Hence to the best of our knowledge the proposed randomized controlled trial represents the first investigation to assess the efficacy and safety of NAC in rhinosinusitis according to current regulatory requirements.

6.4 Pharmacodynamic and Pharmacokinetic Properties

6.4.1 Pharmacodynamics

Data from the Summary of Product Characteristic (SmPC).¹⁵

Acetylcysteine is a derivative of the amino acid cysteine. The efficacy of acetylcysteine is secretolytic and secretomotoric in the area of the respiratory tract. It is discussed that it splits off the interconnecting disulphide bonds between the mycopolysaccharide chains and that it has a depolymerizing effect on DNA-chains (in purulent mucus). Due to these mechanisms, the viscosity of mucus should be reduced.

An alternative mechanism of acetylcysteine is meant to be based on the capacity of its reactive SH group to bind chemical radicals and to detoxify them in this way.

Furthermore, acetylcysteine contributes to an increase in glutathione synthesis, which is important for the detoxification of noxae. This provides the explanation for its antidotal effect in paracetamol intoxication.

A protective effect on the frequency and severity of bacterial exacerbations – when acetylcysteine is administered prophylactically - is described in patients with chronic bronchitis/mucoviscidosis.

6.4.2 Pharmacokinetics

*Absorption*¹⁵

Following oral administration, acetylcysteine is rapidly and almost completely absorbed and metabolized in the liver to cysteine, the pharmacologically active metabolite, as well as to diacetylcysteine, cystine and further mixed disulphides.

*Distribution*¹⁵

Due to the high first-pass effect, the bioavailability of orally administered acetylcysteine is very low (approx. 10%). In humans, maximum plasma concentrations are achieved after 1-3 hours with the maximum plasma concentration of the metabolite cysteine in the range of approx. 2 µmol/l. The protein binding of acetylcysteine was determined to be about 50%.

*Biotransformation*¹⁵

Acetylcysteine and its metabolites occur in three different forms in the organism: partially in free form, partially bound to proteins via labile disulphide bonds and partially as incorporated amino acid. Acetylcysteine is excreted almost exclusively in the form of inactive metabolites (inorganic sulphates, diacetylcysteine) via the kidneys. The plasma half-life of acetylcysteine is approximately 1 hour and is mainly determined by the rapid hepatic biotransformation. Impaired hepatic function therefore leads to prolonged plasma half-lives of up to 8 hours.

*Elimination*¹⁵

Pharmacokinetic studies with intravenous administration of acetylcysteine revealed a distribution volume of 0.47 l/kg (in total) or 0.59 l/kg (reduced); the plasma clearance was determined to be 0.11 l/h/kg (in total) and 0.84 l/h/kg (reduced), respectively. The elimination half-life after intravenous administration is 30-40 minutes while excretion follows three-phase kinetics (alpha, beta, and terminal gamma phase).

Acetylcysteine crosses the placenta and is detected in cord blood. No information is available regarding excretion into breast milk.

No knowledge is available concerning the behaviour of acetylcysteine at the blood-brain barrier in humans.

7 Trial Objectives

7.1 Primary Objective

The primary objective of the present trial is the assessment of the efficacy of three different total daily doses of the investigational product containing 600 mg acetylcysteine per effervescent tablet compared to placebo for the treatment of acute uncomplicated rhinosinusitis.

7.2 Secondary Objectives

The secondary objective of the present trial is the assessment of safety and tolerability of three different total daily doses of the investigational product containing 600 mg acetylcysteine per effervescent tablet compared to placebo for the treatment of acute uncomplicated rhinosinusitis.

8 Investigational Plan

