	
Safety: The Safety Set will be used for the analysis of the safety data. All safety data obtained in this trial will be tabulated descriptively with descriptive group statistics (mean, standard deviation, minimum, maximum, number of valid cases) where appropriate. This will include also the overall assessment of tolerability by the patient and by the investigator on Day 7 (Visit 4) and Day 15 (Visit 6).
 
AEs will be summarized by primary system organ class (SOC) and preferred term (PT). Severity and drug-event relationship of treatment emergent AEs are summarized separately. All adverse events will be listed.
 
Vital signs, including changes from baseline will be summarized. A frequency table will be presented for abnormal values of laboratory parameters.
															

CALCULATION OF SAMPLE SIZE
	
The sample size is calculated in respect of the primary endpoint. For the calculation of sample size, the following parameters were taken into consideration based on data published by Jund et al. (2015)¹:
 
 
 α	= 0.05 (two-sided)	
 
 β	= 0.20 (power = 80%)	
 
 mean MSS change (test)	= 5.4	
 
 mean MSS change (placebo)	= 4.5	
 
 Standard deviation	= 3.4	
 
 Randomization ratio	= 1 (1:1:1:1, 3 doses of test vs. placebo)	
 
 Sample size per group:	= 225 subjects	
 
 
The numbers above refer to the FAS.
 
The number of patients to be randomized in each of the groups is approximately 225. The total number of patients to be randomized is thus equal to 900.
		α	= 0.05 (two-sided)	β	= 0.20 (power = 80%)	mean MSS change (test)	= 5.4	mean MSS change (placebo)	= 4.5	Standard deviation	= 3.4	Randomization ratio	= 1 (1:1:1:1, 3 doses of test vs. placebo)	Sample size per group:	= 225 subjects
α	= 0.05 (two-sided)															
β	= 0.20 (power = 80%)															
mean MSS change (test)	= 5.4															
mean MSS change (placebo)	= 4.5															
Standard deviation	= 3.4															
Randomization ratio	= 1 (1:1:1:1, 3 doses of test vs. placebo)															
Sample size per group:	= 225 subjects															

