Richter et al.²⁸ recently presented an overview of 17 clinical studies on the use of NAC for CIN in more than 2000 patients. The study medication ranged mostly from 600 mg b.i.d. to 1500 mg b.i.d orally administered. The authors concluded that the low incidence of adverse events associated with NAC forms the basis of its recommendation in the guidelines (Richter and Crannage 2015²⁸). This conclusion is likewise supported by a similar systematic review and meta-analysis by Kang et al. (2015)²⁹, who analyzed 20 randomized controlled studies involving 3466 subjects (1756 assigned to NAC). Subjects received either 2400 mg/d p.o. or 2400 \pm 2000 mg while in one of the studies the dose was even 10000 mg. In CIN the cumulative NAC doses and routes of administration may also reach 6000 mg p.o. as reviewed by Trivedi et al. (2009)³⁰. These authors suggested that in patients at risk of CIN, it is prudent to prescribe NAC 1200 mg orally twice per day for 48 hours without raising any safety concerns.

- **Neuropsychiatric disorders**

In a comprehensive review, Deepmala et al. (2015)³¹ analyzed the state of scientific knowledge for the use of NAC in treating psychiatric and neurological disorders. A total of 65 publications met the inclusion and exclusion criteria for the systematic review.

The number of patients under high-dose NAC was over 1400, the oral dose regimen ranged from 1200 mg/d up to 6000 mg/d, and the duration of studies from 16 days to 60 months. Most of the studies used the dose around 2000–2400 mg per day, which appeared to be effective and well tolerated, with no significant between-group differences observed in most of the controlled trials.

Gastrointestinal symptoms were the most common adverse events, including mild abdominal pain, mild abdominal discomfort, heartburn, flatulence, cramps, nausea, vomiting, and diarrhea.

These results have been confirmed in a recent review by Ooi et al. (2018)³² concluding that oral NAC is safe and well tolerated without any considerable adverse effects. Current evidence supports its use as an adjunctive therapy for psychiatric conditions, administered concomitantly with existing medications, with a recommended dosage between 2000 and 2400 mg per day.

- **Cardioprotection**

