10.4 Statistical Tests

██████████ will write the **Statistical Analysis Plan (SAP)** for the present trial.

Efficacy:

Efficacy of the test product will be shown by testing superiority of the three different doses in a hierarchical test procedure from the highest to the lowest dose compared to placebo.

Hierarchical ordered hypotheses will be tested at the type I error rate of $\alpha=0.05$ (two-sided) until the first non-rejection. No error rate adjustment is required.

The set of hypotheses is as follows:

$$H_{01}: \mu_{2400} = \mu_{PL}$$

$$H_{11}: \mu_{2400} \neq \mu_{PL}$$

$$H_{02}: \mu_{1200} = \mu_{PL}$$

$$H_{12}: \mu_{1200} \neq \mu_{PL}$$

$$H_{03}: \mu_{600} = \mu_{PL}$$

$$H_{13}: \mu_{600} \neq \mu_{PL}$$

Where μ notes “mean change from baseline in the daily MSS over the entire treatment period” for the respective strength.

Superiority of the Test treatment over placebo (PL) is confirmed if the p-value is < 0.05 and a positive treatment effect is shown.

For the primary efficacy an endpoint, analysis of covariance (ANCOVA) will be carried out using treatment and center as factors and baseline MSS as a covariate.

The trial will be powered to demonstrate superiority of the test product over placebo in the primary efficacy endpoint.

The confirmatory analysis of the primary endpoint will be performed in the FAS.

In addition, the analyses used for the primary efficacy endpoint will be performed in the PPS.

This analysis is intended to provide supportive evidence and will be considered descriptive.

Safety:

The Safety Set will be used for the analysis of the safety data. All safety data obtained in this trial will be tabulated descriptively with descriptive group statistics (mean, standard deviation, minimum, maximum, number of valid cases) where appropriate.

AEs will be summarized by primary system organ class (SOC) and preferred term (PT). Severity and drug-event relationship of treatment emergent AEs are summarized separately. All adverse events will be listed.

Vitals signs, including changes from baseline will be summarized. A frequency table will be presented for abnormal values of laboratory parameters.

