6.3 Safety Endpoints

- Incidence and severity of adverse events
- Incidence and severity of drug-related adverse events
- Clinically relevant changes in laboratory parameters, vital signs, physical and ENT examination parameters from Visit 1 to Visit 6 (or early termination)
- Overall assessment of tolerability by patient and by investigator.

7 Statistical Analysis Conventions

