The pre-treatment adverse events which occurred before intake of the first dose of IMP (between screening visit (Visit 1) on Day -1 and Visit 2 on Day 1) will be presented in listings.

The adverse events will be analyzed by means of frequency tables. For an overview a frequency table with numbers of patients affected will be presented by treatment for the categories (Summary of adverse events): total, adverse events leading to discontinuation, serious adverse events, and (serious) adverse events with outcome death.

Further frequency tables will be classified by system organ class (SOC), preferred term (PT) derived from MedDRA and by treatment. The numbers of adverse events as well as the numbers of patients affected will be presented.

Moreover, tables for incidences of adverse events and patients with respect to the following parameters will be created:

- Severity (mild, moderate, severe),
- Relationship between study medication and adverse event (suspected, not suspected),
- Outcome (not recovered / not resolved / unchanged; recovered / resolved, improving/ recovering/ resolving; recovered with sequelae; fatal; condition deteriorating; unknown).

All adverse events will be listed, these listings will be split into three parts containing the following columns:

Part I: Rnd. No. , Report No., Observed AE (in verbatim), Seriousness, Action taken with IMP; Severity, Outcome, Relationship to IMP, Relationship to NIMP

The report number is an identifier for the single adverse events within one patient (chronologically).

This part I will be displayed in two versions:

- first version is sorted by treatment group (where pre-treatment adverse events will be pooled as additional group), random number and report number,
- in the second version the adverse events are sorted by random number and report number.

The second and third part will only be displayed sorted by random number and report number with the following information:

Part II: Rnd. No., Report No., MedDRA Coding: Preferred Term (with Code), Date/Time of onset, Date/Time of end, Last date/time of dose before onset, Last treatment.

Part III: Rnd. No, Report No, Event treatment, Specification of event treatment.

These adverse events will be listed for the safety set. If patients experience adverse events who were not randomized, or had no intake of IMP then further listing for these events will be displayed.

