7.3.3.3 Assessment of Tolerability

The tolerability will be assessed by the investigator and by the patient at Visit 4 and Visit 6. It is rated using a five-point rating scale: ① = very poor, ② = poor, ③ = medium, ④ = good, ⑤ = very good.

The assessments will be listed by patient.

The results will be presented by means of frequency tables by visit and treatment.

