8.3 Listings (Appendix 16.2 of the Clinical Study Report)

Section	Table titles
16.2.1 Discontinued patients	Patients not treated with trial medication (only screened) Listing of drop-outs (withdrawal criteria / premature discontinuation), randomized and treated patients Disposition of patients treated with trial medication per study phase Inclusion criteria not met Exclusion criteria met
16.2.2 Protocol deviations	Protocol deviations
16.2.3 Patients excluded from the efficacy analysis	Patients excluded from the efficacy analysis (Per Protocol Set) Patients excluded from the efficacy analysis (Full Analysis Set)
16.2.4 Demographic data	Demographic data of patients treated with trial medication

Section	Table titles
	
Demographic data of patients not treated with trial medication
 
Life style and habits - Alcohol consumption, safety set
 
Life style and habits - History of drug abuse or use of illegal drugs, safety set
 
Life style and habits - Smoking status, safety set
 
Anamnesis on acute uncomplicated rhinosinusitis, Major Symptom Score, safety set
 
Medical and surgical history, safety set
 
Previous medication, safety set
 
Concomitant medication, safety set
 
Medical or other therapeutic measures, safety set
 
Method of contraception, safety set
 
Vital signs, safety set
 
Physical examination, safety set
 
ENT examination, safety set
 
Assessment of tolerability by patient, safety set
 
Assessment of tolerability by investigator, safety set

16.2.5 Compliance and / or drug concentration data	
Visit dates, safety set
 
Dispensation of blinded medication
 
Return and check of used blinded medication

16.2.6 Individual efficacy response data	
Major Symptom Score (MSS) assessed by the patient
 
Sino-nasal outcome test (SNOT-22) assessed by the patient
 
Assessment of overall response to treatment by the investigator

16.2.7 Adverse event listings	
Display of adverse events, part I, sorted by treatment group, safety set
 
Display of adverse events, part I, safety
 
Display of adverse events, part II, safety set
 
Display of adverse events, part III, safety set (Specification of Event treatment)

Section	Table titles
	Display of serious adverse events, part I, safety set Display of serious adverse events, part II, safety set Display of serious adverse events, part III, safety set (Specification of event treatment)

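### Safety and tolerability versus placebo is the only secondary objective, but the planned outputs give side-by-side group results with no estimate or interval for any difference from placebo

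*Protocol*

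**What the plan says.** **Objective.** Protocol 7.2, repeated in SAP 5.1.2, gives this as the single secondary objective: "assessment of safety and tolerability of three different total daily doses of the investigational product containing 600 mg acetylcysteine per effervescent tablet compared to placebo". No hypothesis, margin or precision target goes with it.

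**Method.** Protocol 10.4 states: "All safety data obtained in this trial will be tabulated descriptively with descriptive group statistics". The protocol synopsis extends this to the tolerability ratings.

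**Adverse events.** SAP 7.3.3.1 says that "a frequency table with numbers of patients affected will be presented by treatment for the categories" total, leading to discontinuation, serious, and fatal. Further tables break events down by organ class and preferred term, and then by severity, relationship and outcome. SAP 7.2.1 specifies that frequency tables carry absolute numbers and percentages.

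**Tolerability.** SAP 6.3 names "Overall assessment of tolerability by patient and by investigator" as a safety endpoint. SAP 7.3.3.3 says: "The results will be presented by means of frequency tables by visit and treatment". The table list in SAP 8.1 (sections 14.3, 14.3.1 and 14.3.2) has no tolerability title. The ratings appear only in SAP 8.3, as two listings, one of them "Assessment of tolerability by patient, safety set".

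**Efficacy, for contrast.** SAP 7.4.2.1 tests each dose against placebo on each day from Day 2 to Day 14 and calls that analysis descriptive. SAP 7.4.2.4 tests responder percentages against placebo.

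**The concern.** The objective is worded as a comparison, and the planned outputs stop one step short of it. A reader of the report will see four columns and must judge by eye whether a dose column differs from the placebo column. Nothing planned says how large an excess was observed or how large an excess the data exclude. That second quantity is what makes a reassuring safety statement informative, because similar percentages in arms of this size do not by themselves rule out a moderate excess.

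The protocol also relies on between-group safety findings from other trials when it argues in section 8.2 that the highest dose is acceptable. It would be consistent for this trial to report the same kind of evidence with its uncertainty.

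**Working it through.** **1. Is any safety contrast planned?** Setting the objective against the outputs:

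| Safety domain | Planned output | Difference or interval versus placebo |
|---|---|---|
| Adverse events (SAP 7.3.3.1) | Frequency tables by treatment; listings | None |
| Tolerability (7.3.3.3) | Frequency tables by visit and treatment; listings | None |
| Vital signs (7.3.3.4) | Group statistics and changes from baseline, by treatment | None |
| Physical and ENT examination (7.3.3.5, 7.3.3.6) | Frequency and shift tables | None |
| Laboratory (7.3.3.7) | Group statistics, frequency and shift tables, by treatment | None |

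The titles in SAP 8.1 add no contrast.

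**2. The arm size.** Protocol 10.5 and SAP 5.4 give a difference of 5.4 − 4.5 = 0.9, SD 3.4, two-sided α = 0.05 and 80% power:

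n = 2 × (1.960 + 0.842)² × 3.4² / 0.9² = 224.03, rounded up to 225 per arm.

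The t-based solution is also 225, with power 80.0%. The stated figure is reproduced. It concerns the symptom score only; no sample size or precision is stated for safety. The Safety Set is every randomized patient who took a dose, so up to about 225 per arm.

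**3. Precision available at 225 per arm.** The documents give no expected event rate for this trial, so a range is assumed, with the same rate p in both arms.

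- Wald half-width: 1.96 × √(2p(1 − p)/225).
- Newcombe interval, from the Wilson limits (l, u) of each arm. With equal counts the half-width is √((p − l)² + (u − p)²).

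Worked example at 5%, taken as 11 of 225 in each arm: p = 4.89%, Wilson limits 2.75% and 8.54%. Half-width = √(2.14² + 3.65²) = 4.2 points.

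| Assumed rate, both arms | Wald half-width (points) | Newcombe half-width (points), at nearest whole count |
|---|---|---|
| 1% | 1.8 | 2.4 (2/225) |
| 5% | 4.0 | 4.2 (11/225) |
| 10% | 5.5 | 5.6 (22/225) |
| 20% | 7.4 | 7.4 (45/225) |
| 25% | 8.0 | 8.0 (56/225) |

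At 5% in both arms, then, the observed difference is zero and the data still allow an excess of up to about 4 points.

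**4. Tolerability.** The text of SAP 7.3.3.3 specifies the analysis, and the list in SAP 8.1 lacks its title. Other outputs promised in the text also have no separate title there: the descriptive statistics of individual laboratory changes (7.3.3.7) and the ENT shift tables (7.3.3.6). The list is therefore not a full inventory, and the tolerability gap is a mismatch between text and list.

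**The case against.** The strongest reply is that the plan does what it says. The objective asks for an assessment, with no hypothesis or margin, and the protocol declares that safety is handled descriptively. Placebo is Group D and so stands as a column in every by-treatment table, with counts and percentages. That is a randomized side-by-side comparison, and a reader could compute an interval from it. This stands: a reader who infers that the objective goes unanswered is going further than the documents support. What it leaves open is that the plan itself reports no estimate or precision, although SAP 7.4.2.1 already accepts unadjusted, descriptive contrasts with placebo for efficacy.

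Three other inferences are tempting and also fail:

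- *That tolerability will have no group result.* SAP 7.3.3.3 commits to frequency tables by visit and treatment, and the synopsis includes the ratings in the tabulation. Only a title is missing.
- *That the protocol identifies gastrointestinal events as the leading reactions at the trial's doses.* The sentence "Gastrointestinal symptoms were the most common adverse events" in Protocol 8.2 summarizes a review of psychiatric and neurological studies at 1200 to 6000 mg/day. That range leaves out the 600 mg arm and extends well above 2400 mg. The product information in Protocol 8.3.1 classes abdominal pain, nausea, vomiting and diarrhoea as uncommon (below 1 in 100) and dyspepsia as rare.
- *That the sponsor plans to conclude no difference from similar percentages.* No section says so.

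**Conclusion.** The point holds as an improvement to the plan and does not show an error in it. The only secondary objective is comparative, and the plan answers it with side-by-side group results that carry no estimate or interval for the difference from placebo.

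The size of what goes unstated is about 2 to 8 percentage points either side of the observed difference. This assumes about 225 dosed patients per arm, 95% intervals, and true event rates between 1% and 25%. The rates are assumptions. At the frequencies in the product information (below 1%) the figure sits at the low end, about 2 points. For a broad category such as any adverse event it would be larger if the rate is higher.

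The missing tolerability title is a separate housekeeping correction.

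**What to change.** 1. Add to SAP 7.3.3.1 and SAP 8.1 one table giving, for each dose versus placebo in the Safety Set, the difference in the percentage of patients with a 95% confidence interval (for example Newcombe). Four rows suffice: any treatment-emergent adverse event, any event with suspected relationship, any event leading to discontinuation, and any event in the gastrointestinal organ class. Label the table descriptive and unadjusted for multiplicity.
2. Add to SAP 8.1 the titles of the tolerability frequency tables (patient and investigator, Visits 4 and 6) already promised in SAP 7.3.3.3. A center-stratified test of the ordinal ratings is not needed.

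The cost is a short SAP edit and a few table programs on data already collected, with no change to sample size or conduct. The downside is 4 × 3 = 12 unadjusted intervals, some of which may exclude zero by chance; the descriptive label is there to stop them being read as tests.
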